7.4.4.4 Alcohol Breath Test

A commercially available breath analyzer (Alcotest 6510, Draeger Safety GmbH) will be used to determine the concentration of alcohol in the subject's breath according to the Schedule of Assessments (see Table 1).

Additional alcohol breath tests during the trial are at the discretion of the Investigator.

7.5 Pharmacokinetics

7.5.1 Blood Sampling

On the PK profiling day, an indwelling venous catheter will be positioned in a suitable forearm vein for blood sampling and should be kept, if possible, until at least 24 h after dosing. After removing the indwelling venous cannula, samples will be taken by venipuncture.

At visits where assessment time points coincide with each other, the vital signs and ECG assessments should be performed slightly before the specific time point and the PK blood sampling should be performed on time.

Plasma concentrations of tepotinib and its metabolites MSC2571109A and MSC2571107A will be determined in each period according to the sampling schedule outlined in the Schedule of Assessments (see [Table 1](#)). The exact date and time of sample collection must be recorded in the eCRF and will be used in the calculation of PK parameters. Blood samples should be taken as close as possible to the scheduled time points. Samples taken outside of the time periods shown in Table 3 need an explanation and will be considered as protocol violation.

Table 3 Time Windows

Planned Blood Sampling	Time Windows (min)
Pre-dose	- 60
0.25 - 1 h post-dose	± 2
> 1 h - 12 h post-dose	± 5
> 12 h - 48 h post-dose	± 15
> 48 h - 168 h post-dose	± 30

Concentrations of tepotinib and its metabolites MSC2571109A and MSC2571107A will be measured using validated liquid chromatography-tandem mass spectrometry methods at Nuvisan. The assays will be carried out in accordance with Good Laboratory Practice regulations and the EMA reflection paper. A separate bioanalytical protocol will be provided before the start of the analytical part of the trial. Full details of the bioanalytical method used will be described in a separate bioanalytical report.

7.5.2 Calculation of Pharmacokinetic Variables

Noncompartmental computation of PK parameters will be performed using the software Phoenix® WinNonlin® 6.4 or higher (Certara, L.P., Princeton, New Jersey). For definitions of PK parameters, see [Table 4](#).

Table 4 **Definition of PK Parameters for Tepotinib and its Metabolites After Single Dose Administration**

Symbol	Definition
AUC _{0-t}	Area under the plasma concentration-time curve (AUC) from time zero (= dosing time) to the last sampling time (t_{last}) at which the concentration is at or above the lower limit of quantification (LLOQ), calculated per the mixed log linear trapezoidal rule (ie linear up/log down)
AUC _{0-∞}	Area under the plasma concentration-time curve from time zero (= dosing time) extrapolated to infinity, calculated as $AUC_{0-t} + AUC_{extra}$. AUC_{extra} represents the extrapolated part of $AUC_{0-∞}$ calculated by $C_{last,pred}/\lambda_z$, where $C_{last,pred}$ is the predicted plasma concentration at the last sampling time point, calculated from the log-linear regression line for λ_z determination at which the measured plasma concentration is at or above LLOQ
C _{max}	Maximum plasma concentration observed
t _{last}	The last sampling time at which the concentration is at or above the lower limit of quantification
t _{max}	Time to reach the maximum plasma concentration
t _{1/2}	Terminal half-life, calculated as $\ln 2/\lambda_z$
λ_z	Terminal rate constant determined from the terminal slope of the log-transformed plasma concentration curve using linear regression on terminal data points of the curve
CL/f	Apparent total body clearance of drug from plasma following oral/extravascular administration, calculated as dose/AUC _{0-∞} , only parent drug, will not be calculated for the metabolites
V _{z/f}	Apparent volume of distribution during the terminal phase following oral/extravascular administration, will not be calculated for the metabolites
AUC _{extra}	The AUC from time t_{last} extrapolated to infinity
AUC _{extra%}	$AUC_{extra\%} = (AUC_{extra} / AUC_{0-∞}) \times 100$

Individual PK parameters will be calculated using actual sampling times. The pre-dose sample will be considered as if it had been taken simultaneously with the administration of study drug. PK variables will be evaluated and listed for all subjects who provide sufficient concentration-time data.

Concentrations below the lower limit of quantification (< LLOQ), which are before the last quantifiable data point, will be taken as zero for calculating the AUC.

7.6 Biomarkers

Biomarkers are not determined in this trial.

7.7 Pharmacogenetics

Pharmacogenetic sampling is mandatory for trial participation. An additional separate ICF will be used. One blood sample should be collected in duplicate on Day -1 of the first treatment period prior to administration. The pharmacogenetic samples will be analyzed conditionally in case of unexpected PK profiles. The results of the PGx analysis, as applicable, will be described in a separate report.

Storage and analyses of samples will be handled according to the specifications described in the ICF.

7.8 Other Assessments

Not applicable.

8 Statistics

8.1 Statistical Hypotheses

Part A

The following null hypothesis for the ratio of the geometric means (GeoMean) will be used to assess bioequivalence

$H_0: \mu_T/\mu_R \leq 0.8000$ or $1.2500 \leq \mu_T/\mu_R$ for at least one parameter (AUC_{0-t} or AUC_{0-∞} or C_{max})

$H_1: 0.8000 < \mu_T/\mu_R < 1.2500$ for all parameters (AUC_{0-t} and AUC_{0-∞} and C_{max})

where μ_T and μ_R are the geometric means for the test and reference treatment respectively.

The test treatment is the new tablet formulation (TF3) and reference is the tablet formulation used in clinical studies (TF2) both under fasting condition.

The null hypothesis will be tested using a two-stage adaptive design.

Parts B and C

[figure not shown]
The statistical analysis of study data will be descriptive; no hypothesis tests will be performed.

8.2 Sample Size

8.2.1 Part A (Bioequivalence)

Part A of the study is planned as a two-stage adaptive design (see [Figure 3](#)) due to the residual risk with respect to the unknown PK-variability of tepotinib in the fasted state. The procedure will follow the method C described by Montague [\[4\]](#) and Potvin [\[5\]](#). For the first stage, the trial will be sufficiently powered to show bioequivalence based on an assumption for PK-variability in the fasted state (reliable data not available).

Figure 3 **Diagram of Two-Stage Adaptive Design**

Source: (Montague et al [4]) [Figure 2](#); BE: Bioequivalence

The total and mixed intrasubject variabilities CVs (%) observed most recently for AUC_{0-t} and C_{max} of tepotinib are summarized in Table 5.

Table 5 **Overview of the PK-Variability Observed in the Previous Tepotinib Studies**

Study	Formulation Dose (Condition)	Arm	AUC_{0-t}		C_{max}	
			Total Geometric CV%	Mixed intra- individual CV%	Total Geometric CV%	Mixed intra- individual CV%
EMR200095-002	TF1 - 30 mg (fed vs. fasted)	TF1 Fed	12.9%		14.8%	
		TF1 Fasted	18.3%	11.1%	28.2%	23.7%
EMR200095-007	CF2 vs. TF1 30 mg (fed)	CF2	28.7%		30.4%	
		TF1	21.4%	12.2%	26.3%	12.8%
EMR200095-0012	TF1 vs. TF1* 100 mg (fed)	TF1	20.4%		22.8%	
		TF1*	24.8%	10.0%	29.5%	12.7%
EMR200095-0012	TF1 vs. TF2 500 mg (fed)	TF1	24.0%		19.8%	
		TF2	27.0%	10.1%	26.2%	12.6%

AUC_{0-t} = area under the plasma concentration-time curve from time zero to the last sampling time at which the concentration is at or above the lower limit of quantification, CF2 = Capsule Formulation 2; C_{max} = maximum plasma concentration, CV = coefficient of variation, PK = pharmacokinetics, TF1 = Tablet Formulation 1; TF1* = Tablet Formulation 1 with finely micronized active pharmaceutical ingredient; TF2 = Tablet Formulation 2.

Overall, the total variability in AUC and C_{max} in the fed state was between 12.9% and 26.3% for the formulation TF1. The mixed intrasubject variabilities of AUC and C_{max} were largely dose-independent ranged between 10.0% and 12.8% in the fed state across all the investigated doses.

AUC total variability was similar between TF1 and TF2 at the dose of 500 mg but C_{max} variability was somewhat higher for TF2.

Only one study (EMR200095-002) investigated tepotinib under fasted condition. The maximum value for the mixed intrasubject variability was observed for C_{max} (CV of 23.7%). As no data is available for the 500 mg dose level under fasted conditions, the CV value is assumed to be around 24% for C_{max} and slightly lower for AUC in this study.

With these assumptions, an assumed geometric mean ratio Test/Reference (GMR T/R) of 0.95, a one-sided alpha level of 0.05, 36 evaluable subjects will be needed to provide approximatively 90% power to show bioequivalence already in the first stage. A drop-out compensation of 4 subjects will be added.

With a CV of 29%, the sample size of 36 evaluable subjects would still result in approximately 80% power to show bioequivalence in the first stage.

The second stage will be performed only, if after Stage 1 the PK-variability turns out to be larger than initially assumed as specified in [Figure 3](#) (if power is less than 80% and bioequivalence criteria are not met in Stage 1 with an alpha of 0.0294). For Stage 2, the sample size will be adjusted based on the newly estimated PK-variability (maximum CV (%) value of the 3 PK primary endpoints), a targeted power of 80% and an adjusted alpha of 0.0294. The GMR T/R will be assumed to be 0.95 and will **not** be adjusted for the second stage.

As reported in Potvin [\[5\]](#) Table I and Table II for method C, with a first stage sample size of 36 subjects under the assumptions of a CV value of 20% (lower than the assumed CV of 24%), and a GMR of 0.95, the power to show bioequivalence will be approximately 98% and the probability of proceeding to Stage 2 will be 0.0%. With a first stage sample size of 36 subjects under the assumptions of a CV value of 30% (higher than the assumed CV of 24%), and a GMR of 0.95, the power to show bioequivalence will be less than 90% and the probability of proceeding to Stage 2 will be 22.7%. Table 6 summarizes the probability, mean total sample size (n) to proceed to Stage 2 for CV values up to 50% and the estimated overall power for both stages when considering a first stage sample size of 36 subjects.

Table 6 Power and Mean n for Declaring Bioequivalence for Individual PK Parameters

Sample size Stage 1 (n_1)	CV (%)	% Studies in Stage 2	Mean n	Power (%)
36	20	0.0	36.0	98
36	30	22.7	40.5	85
36	40	65.9	67.3	82
36	50	90.8	112.6	81

CV = coefficient of variation, n = total number of subjects, PK = pharmacokinetics

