16.1.1 Primary Endpoints

16.1.1.1 Primary Endpoints in Part A

Statistical Hypotheses for Part A (Bioequivalence) - Two-stage Adaptive Design

The following null hypothesis for the ratio of the geometric means will be used to assess bioequivalence

$H_0: \mu_T/\mu_R \leq 0.8000$ or $1.2500 \leq \mu_T/\mu_R$ for at least one parameter (AUC_{0-t} or $AUC_{0-\infty}$ or C_{max})

$H_1: 0.8000 < \mu_T/\mu_R < 1.2500$ for all parameters (AUC_{0-t} and $AUC_{0-\infty}$ and C_{max})

[figure not shown]
where μ_T and μ_R are the geometric means for the test and reference treatment respectively.

The test treatment is the new tablet formulation (TF3) and reference is the tablet formulation used in clinical studies (TF2) both under fasting condition.

The null hypothesis will be tested using a two-stage adaptive design [Figure 1](#). The procedure will follow the method C described by Montague [1] and Potvin [2].

Figure 1

Diagram of Two-Stage Adaptive Design

Source: (Montague et al [1]) Figure 2; BE: Bioequivalence

The power at stage 1 will be estimated using a geometric mean ratio (GMR) of 0.95 and CV(%) as the maximum intra-individual CV(%) for the three PK parameters C_{max} , AUC_{0-t} , and $AUC_{0-\infty}$. The CV(%) for each parameter will be estimated by analysis of variance (ANOVA) on the log transformed parameter. The ANOVA will include TREATMENT, PERIOD, SEQUENCE and SUBJECT within SEQUENCE as fixed effects.

If the power is $\geq 80\%$ then bioequivalence will be evaluated at an alpha level of 0.05. If the power is $< 80\%$ and the bioequivalence criteria not met at an alpha level of 0.0294, the study will proceed to the second stage with a re-estimated sample size. The re-estimated sample size will be the minimum even number of subjects required for the combined data from stages 1 and 2 to have at least 80% power (based on the newly estimated CV[%], an assumed GMR of 0.95 and an adjusted alpha of 0.0294.).

The significance level for the second stage analysis will be set to 0.0294.

The null hypothesis will be rejected if the CI corresponding to the α -level (either 90% or 94.12%) for the ratio of the geometric mean lies within the interval 0.8000 to 1.2500.

Analyses in Part A

Primary analysis

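### The Stage 1 power figures for Part A are for one parameter at a fixed alpha of 0.05, not for the joint hypothesis under method C; the CV 29% figure is materially too favourable

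*Protocol*

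**What the plan says.** Protocol 8.1 and SAP 16.1.1.1 define success jointly: the ratio must lie between 0.80 and 1.25 "for all parameters", that is, for AUC0-t, AUC0-∞ and Cmax together.

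Protocol 8.2.1 plans on "an assumed geometric mean ratio Test/Reference (GMR T/R) of 0.95" and states that "the CV value is assumed to be around 24% for C_{max} and slightly lower for AUC in this study". At a one-sided alpha of 0.05, it concludes that "36 evaluable subjects will be needed to provide approximatively 90% power to show bioequivalence already in the first stage". It then adds a reassurance for higher variability: at a CV of 29%, "36 evaluable subjects would still result in approximately 80% power to show bioequivalence in the first stage".

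Table 6 is titled as applying to individual PK parameters. The two Stage 1 sentences carry no such qualifier, and Table 6 has no row for CV 24% or 29%.

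The Stage 1 power check uses the largest CV of the three parameters. If estimated power is below 80%, alpha becomes 0.0294. If bioequivalence is then not shown, the SAP re-estimates the sample size as the "minimum even number of subjects required for the combined data from stages 1 and 2 to have at least 80% power", again from that one CV.

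**The concern.** A reader takes power to show bioequivalence to mean the chance that the hypothesis in 8.1 is accepted. The stated figures differ from that in two ways.

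- They use one CV and one ratio. The chance that all three parameters pass cannot exceed the chance for the least favourable one, and it is lower unless the AUC tests are almost sure to pass. By planning on an AUC CV only slightly below that of Cmax, the protocol does not assume this.
- They hold alpha at 0.05, whereas method C switches to 0.0294 in trials whose estimated power falls below 80%. A true CV of 29% lies almost exactly at that switch.

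At stake is how the sponsor judges the chance of finishing after Stage 1 and of needing Stage 2. The validity of the test is not in question.

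**Working it through.** **Inputs from the documents:** n = 36 evaluable, 2×2 crossover, GMR 0.95, limits 0.80–1.25, one-sided alpha 0.05 or 0.0294, CV 24% or 29%, AUC CV slightly lower (no number).

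**Assumptions, not in the documents:** GMR 0.95 for all three parameters; within-subject correlation 0.98 between AUC0-t and AUC0-∞; 0.5 to 0.9 between Cmax and AUC; both AUCs with the same CV.

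**Step 1. Reproduce the stated figures.** σ = √ln(1 + CV²), SE = σ√(2/n), df = n − 2 = 34, t(0.95) = 1.691. Two one-sided tests, integrated over the chi-square distribution of the variance estimate.
- CV 24%: σ = 0.2366, SE = 0.0558, power 91.5% (stated about 90%). With n = 34 it is 89.9%, so 36 is the smallest even n reaching 90%.
- CV 29%: σ = 0.2842, SE = 0.0670, power 79.9% (stated about 80%).

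Both stated figures are therefore correct single-parameter powers at alpha 0.05.

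**Step 2. Find the switch.** With n = 36, power equals 80% at a CV of 28.95%. Above that estimated CV, alpha is 0.0294 (t = 1.955). If the true CV is 29%, the estimate exceeds 28.95% in about 47% of trials (34 df). If it is 24%, this happens in about 5%.

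**Step 3. Simulate Stage 1** (300,000 trials per scenario; normal log-ratios, Wishart variances). Each joint range runs over Cmax–AUC correlation 0.5 to 0.9. In the method C columns, alpha depends on the estimated CV: that of Cmax for one parameter, the largest of the three for the joint result.

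| Cmax CV | AUC CV | One parameter, alpha 0.05 | Joint, alpha 0.05 | One parameter, method C | Joint, method C |
|---|---|---|---|---|---|
| 24% | 23% | 91.5% | 86–89% | 91% | 85–89% |
| 24% | 22% | 91.5% | 87–90% | 91% | 87–90% |
| 24% | 19% | 91.5% | 90–91% | 91% | 90–91% |
| 29% | 23% | 79.9% | 76–79% | 75% | 70–74% |
| 29% | 26% | 79.9% | 72–77% | 75% | 65–72% |
| 29% | 28% | 79.9% | 68–75% | 75% | 60–68% |

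**Step 4. Both stages together** (40,000 trials per scenario; total n re-estimated from the largest CV, pooled analysis at 0.0294). For one parameter at CV 30%, the calculation gives 22.0% of trials in Stage 2, mean n 40.3 and power 84.7%; Table 6 has 22.7%, 40.5 and 85%. Jointly, overall power is:
- 79–83% at Cmax 30%/AUC 27% (Table 6: 85%)
- 76–80% at 40%/36% (Table 6: 82%)
- 80–83% at 29%/26% and 78–82% at 29%/28% (one parameter at 29%: 85%)

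The probability of entering Stage 2 at 30%/27% is about 25–32%, against 22.7% in Table 6.

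**The case against.** The strongest reply is that nothing was miscalculated. Both figures reproduce, the alpha of 0.05 is stated, Table 6 is labelled as per-parameter, and both documents say that the largest of the three CVs drives the adaptation. All of that stands: this is a gap between what the figures describe and what the text says they describe.

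The second reply is that the CV 24% figure is hardly overstated. The mixed intra-individual AUC CVs in Table 5 are 10.0–12.2%. In the 500 mg TF1 versus TF2 comparison (fed), the AUC-to-Cmax ratio is 10.1/12.6 = 0.80, which implies an AUC CV of 0.80 × 24% = 19.2% and a joint power of 90–91%. In the only study with a fasted arm the ratio is 11.1/23.7 = 0.47, and there would be no joint loss at all. This also stands, although Table 5 is background: the protocol planned on a value slightly below 24%. It does not rescue the 29% sentence, because the change of alpha alone brings one parameter down to about 75%.

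The third reply is that the SAP's 80% is a step in a re-estimation algorithm with its inputs stated, not a promise of joint success. That is fair, and it is why one clarifying sentence suffices there.

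A reader might infer that the shortfall is worst near CV 29%. It is not. With AUC CV at 0.9 times Cmax CV, the Stage 1 gap at alpha 0.05 is about 2.5–8 points at 29%, 5–13 at 35% and 6–17 at 40%. Nor would it be enough to replace 80% by the fixed-alpha joint figure (72–77% at AUC CV 26%), since that still ignores the switch to 0.0294.

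**Conclusion.** The point holds for the labelling of both figures, and it is material for CV 29%. At CV 24%, about 90% is at most a few points too favourable, and it is right if AUC CV is about 19% or less. At CV 29%, the design does not deliver about 80% Stage 1 success: it is about 75% for one parameter, about 70–74% jointly with AUC CV 23%, and about 60–72% jointly with AUC CV 26–28%.

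The direction of the joint effect is certain. Its size is not fixed by the documents, because it rests on the assumed AUC CVs, the correlations and a common GMR of 0.95. The fall to 75% for one parameter needs none of the AUC or correlation assumptions.

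A reader might conclude that 36 subjects are too few or that Part A is underpowered overall. The documents do not support this: Stage 2 brings joint overall power back to about 78–83% at Cmax CV 29% with AUC CV 26–28%, close to the 80% target. Nor is type I error at issue, since requiring all three parameters to pass needs no alpha adjustment.

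**What to change.** Keep the sample size, the analysis and the decision rule.

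- **Protocol 8.2.1:** label the 90% and 80% figures as per-parameter power at alpha 0.05. Replace or supplement them with joint Stage 1 success under the method C alpha rule, over a stated range of AUC CV and Cmax–AUC correlation that includes the case where Cmax alone decides.
- **Table 6:** add a joint column under the same stated assumptions.
- **SAP 16.1.1.1:** state that the 80% re-estimation target applies to the single most variable parameter, not to the joint hypothesis.

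The cost is one short simulation and a few sentences. The downside is that the stated figures become less favourable. No subjects are added.

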8.6.2 Analysis of Primary Endpoints

Part A

An analysis of variance (ANOVA) model will be fitted for the log-transformed PK parameters C_{\max} , AUC_{0-t} , $AUC_{0-\infty}$ based on the PK analysis set. The model will include treatment, period, sequence and subject within sequence as fixed effects. If a Stage 2 is required and the number of subjects in Stage 2 is sufficiently large, stage will be included as additional effect in the ANOVA model for the analysis of the pooled data of both stages. More details will be given in the SAP.

Treatment differences on the log scale of tepotinib will be estimated for C_{\max} , AUC_{0-t} , $AUC_{0-\infty}$ together with their CIs with coverage probability according to the planned 2-stage procedure in [Figure 3](#). Point estimates and CIs will be back-transformed to the original scale for the comparisons. The variance estimate from Stage 1 will be used to evaluate the power at Stage 1.

The comparison will be the new tablet formulation (TF3) vs the tablet formulation used in clinical studies (TF2) under fasting condition.

Bioequivalence will be assessed after Stage 1 using Stage 1 data, or after Stage 2 using the pooled data of both stages.

The null hypothesis will be rejected if the CI corresponding to the α -level in the [Figure 3](#) (either 90% or 94.12%) for the ratio of the GeoMean lies within the interval 0.8000 to 1.2500.

Parts B and C

A mixed model with treatment, period and sequence as fixed effects and a random effect for subject within sequence will be applied to log-transformed PK parameters C_{max} , AUC_{0-t} , and $AUC_{0-\infty}$ based on the PK analysis set. Treatment differences on the log scale of tepotinib will be estimated for C_{max} , AUC_{0-t} , and $AUC_{0-\infty}$ together with their 90% CIs. Point estimates and CIs will be back-transformed to the original scale for the comparisons:

- Part B: Tepotinib PK parameters after administration of the tablet formulation TF2 under fasting administration vs tepotinib TF2 after a high fat, high calorie breakfast
- Part C: Tepotinib PK parameters after administration of the tablet formulation TF3 under fasting administration vs tepotinib TF3 after a high fat, high calorie breakfast.

Individual estimates of relative bioavailability will be calculated for each subject.

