8.6.4 Analysis of Safety and Exploratory Endpoints

Safety data analysis will be conducted on the Safety Analysis Set of each part. The number and percentage of subjects experiencing at least 1 TEAE will be summarized by treatment as will the number of events. Tables by relationship to study drug and by severity will be generated. AEs will be coded using Medical Dictionary for Regulatory Activities terminology. All laboratory data will be reported with SI units.

Laboratory parameters will be summarized using descriptive statistics for absolute values and change from baseline over time, by post-dose shifts relative to baseline, and data listings of clinically significant abnormalities/out of the normal range.

Vital signs and ECG data will be summarized by changes from baseline values by treatment using descriptive statistics. Clinically significant ECG findings for individual subjects will be listed and summarized as appropriate.

PK concentrations will be descriptively summarized. Individual and mean concentration-timeplots will be produced in linear and log-linear scale.

Exploratory endpoints will be analyzed with descriptive statistics.

8.7

Interim and Additional Planned Analyses

A two-stage design is used in Part A. Based on the measured variability, the corresponding power for the number of subjects in Stage 1 will be estimated. If the power is < 80%, an interim analysis will be performed. The significance level for both the interim analysis and the final analysis will then be set to 0.0294. For details refer to section 8.6.2.

9

Ethical and Regulatory Aspects

9.1

Responsibilities of the Investigator

The Investigator is responsible for the conduct of the trial at the site and will ensure that the trial is performed in accordance with this protocol, the ethical principles outlined in the Declaration of Helsinki, ICH GCP [7], and any other applicable regulations. The Investigator must ensure that only subjects who have given informed consent are included in the trial.

9.2

Subject Information and Informed Consent

An unconditional prerequisite for each subject prior to participation in the trial is written informed consent, which must be given before any trial-related activities are carried out. Adequate information must therefore be given to the subject by the Investigator or an appropriate designee (if local regulations permit) before informed consent is obtained.

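### The 80% Stage 1 power quoted at CV 29% is fixed-sample power at alpha 0.05; under the planned Method C rule the chance of showing bioequivalence in Stage 1 is about 75% for one PK parameter

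*Protocol*

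**What the plan says.** Protocol Section 8.2.1 plans Part A as a two-stage design following Method C. The Stage 1 size is set for a CV of about 24% and a GMR of 0.95: "a one-sided alpha level of 0.05, 36 evaluable subjects will be needed" for roughly 90% power, with four more subjects added for drop-out. The next paragraph gives one less favourable case, a CV of 29%, and states that "the sample size of 36 evaluable subjects would still result in approximately 80% power to show bioequivalence in the first stage".

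The testing rule follows. Stage 2 is run only "if power is less than 80% and bioequivalence criteria are not met in Stage 1 with an alpha of 0.0294". Section 8.6.2 adds: "The variance estimate from Stage 1 will be used to evaluate the power at Stage 1". Section 8.7 covers the case of estimated power below 80%: "The significance level for both the interim analysis and the final analysis will then be set to 0.0294". SAP Section 16.1.1.1 gives the other branch: if estimated power is at least 80%, "then bioequivalence will be evaluated at an alpha level of 0.05".

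Table 6 ("Power and Mean n for Declaring Bioequivalence for Individual PK Parameters") reports, for Method C with 36 subjects in Stage 1, the share of studies entering Stage 2, the mean total n and the overall power. At CV 30%, "the probability of proceeding to Stage 2 will be 22.7"%, mean n is 40.5 and overall power is 85%. The table has no row for CV 29% and no column for Stage 1 success.

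**The concern.** The CV 29% sentence describes an outcome, bioequivalence shown in Stage 1, but its figure assumes that Stage 1 is always tested at 0.05. Under the planned rule that is not certain. With 36 subjects, the CV at which estimated power drops to 80% is almost exactly 29%, so at this true CV nearly half of all trials would be tested at the stricter level.

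The two-stage design was chosen because fasted variability was uncertain, and CV 29% is the only higher-CV case for which the protocol gives a power for Stage 1. A planner would take from it a 20% chance of not succeeding in Stage 1, when under the planned rule the chance is about 25%.

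**Working it through.** **Inputs.** 36 evaluable subjects, GMR 0.95, one-sided alpha 0.05, CV 24% and 29% (Protocol 8.2.1); limits 0.8000 to 1.2500 (Protocol 8.6.2); two sequences at 1:1 (Protocol 8.3), so 34 error degrees of freedom; alpha 0.05 or 0.0294 according to estimated power (Protocol 8.2.1 and 8.7, SAP 16.1.1.1).

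**Assumption.** The alpha used in the Stage 1 power check is not stated in the text, and the design figure is not reproduced in the copy reviewed. I take 0.05, test that choice against Table 6, and give the alternative.

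**Formulas.** Log-scale within-subject variance: s² = ln(1 + CV²). Standard error of the treatment difference: √(2s²/36). Power is the probability that both one-sided tests reject, integrated over the chi-square distribution (34 df) of the variance estimate.

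**Step 1: reproduce the protocol's figures.** At CV 29%, s² = ln(1 + 0.29²) = 0.0808 and SE = √(2 × 0.0808/36) = 0.0670.

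| CV | Power at alpha 0.05 | Stated | Power at alpha 0.0294 |
|---|---|---|---|
| 24% | 91.5% | about 90% | 86.4% |
| 29% | 79.9% | about 80% | 71.0% |

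The stated values are therefore fixed-sample power at alpha 0.05.

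**Step 2: find the switch point.** With n = 36, GMR 0.95 and alpha 0.05, estimated power equals 80% at an observed CV of 28.95%. At a true CV of 29%, the observed CV is at or below this in 52.7% of trials (tested at 0.05) and above it in 47.3% (tested at 0.0294).

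**Step 3: Stage 1 under Method C, CV 29%.** Split the Step 1 integral at the switch point, using 0.05 below it and 0.0294 above it.

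- Bioequivalence shown at 0.05: 44.5%
- Bioequivalence shown at 0.0294: 30.1%
- Stage 1 success: 44.5% + 30.1% = **74.6%**
- Stop without success: 52.7% − 44.5% = 8.2%
- Go to Stage 2: 47.3% − 30.1% = 17.2%

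Simulating both stages gives the same Stage 1 success, a further 10.9% succeeding in Stage 2, and overall power of 74.6% + 10.9% = 85.5%.

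**Step 4: other CVs, same method.** At CV 24%, Stage 1 success is 91.0% against 91.5% nominal. At CV 30% it is 35.1% + 35.5% = 70.6% against 77.2% nominal. Stage 1 success is at least 80% only up to a CV of about 27.6%.

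**Step 5: check against Table 6, CV 30%.** Computed share entering Stage 2 is 22.3% (stated 22.7%), simulated mean n 40.5 (40.5) and overall power 84.9% (85%). If the power check used 0.0294, the switch would be at an observed CV of 26.2% and 28.9% would enter Stage 2 at CV 30%, which does not fit the table. Stage 1 success at CV 29% would then be 72.4%.

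**Step 6: three parameters.** These figures are for one parameter, as in Table 6. The plan branches on the largest of the three CVs and requires all three parameters to pass. Any trial that meets this would also have passed on the single parameter alone, so joint Stage 1 success cannot be higher. How much lower it is depends on correlations that the documents do not give.

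**The case against.** The strongest reply is that these documents use Stage 1 power to mean the nominal power of the Stage 1 sample. Protocol Section 8.7 and SAP Section 16.1.1.1 both use it that way for the branching decision. Read so, the sentence marks the CV at which nominal power falls to 80%, which is the Method C switch point, and it is right. This explains where the 80% came from. It does not make it the chance of showing bioequivalence in the first stage, which is what the sentence says.

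A reader might infer that the basis was concealed. The documents do not support that: alpha 0.05 is stated in the paragraph before, and the later figures are introduced as Method C results. Table 6 also limits over-reading, since 22.7% entering Stage 2 at CV 30% caps Stage 1 success there at 77.3%.

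One could also point to the 40 subjects randomised. If all 40 were evaluable, Stage 1 success at CV 29% would be 80.9%. But the sentence specifies 36 evaluable, and the other four are drop-out allowance.

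Finally, no decision rests on the figure. That is true, and it sets the severity.

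**Conclusion.** The point holds as a minor correction. As a statement about Stage 1 success under the planned rule, the 80% at CV 29% is about 5 points too high (79.9% − 74.6% = 5.3). The result rests on a GMR of 0.95, 36 evaluable subjects, a single PK parameter, and a Stage 1 power check at alpha 0.05; with a check at 0.0294 the figure is about 72%, so the conclusion stands either way.

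A reader might go further and infer that the power calculation is wrong or that Part A is underpowered. Neither follows. The 80% reproduces from its stated inputs, the size of 36 comes from the CV 24% case where the two bases nearly agree, and overall two-stage power at CV 29% is about 85%, above the 80% target.

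**What to change.** Restate the CV 29% sentence in Protocol Section 8.2.1, for example:

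> With a CV of 29%, 36 evaluable subjects give a nominal single-stage power of approximately 80% at alpha 0.05; under Method C the probability of showing bioequivalence in Stage 1 is about 75% for an individual PK parameter, with overall power of about 85% across both stages.

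Before using the 75%, the sponsor should confirm that the Stage 1 power check is made at alpha 0.05. The cost is one sentence of wording. Sample size, alpha levels, decision rule, conduct and analysis stay as they are.
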